10.4 Compensation of injury

The sponsor/investigator has a liability insurance, which is in accordance with article 7 subsection 6 of the WMO. As this study compares two ventilation strategies used for standard care an exception from the requirement for insurance to cover for damage to research subjects through injury or death caused by the study is applicable.

11. ADMINISTRATIVE ASPECTS, MONITORING AND PUBLICATION

11.1 Handling and storage of data and documents

All patients will be addressed to the inventories with a random patient identification code. The codebook will be stored digitally and in paper. The paper version will be stored behind a lock and the digital form will be encrypted with a double password. All data will be stored for the length of the study and for 15 years afterwards. All handling of personal data will comply with the Dutch Personal Data Protection Act.

11.2 Monitoring and Quality Assurance

Queries on the database will be done by a statistician and analyzed by the monitor to signalize early aberrant patterns, trends, issues with consistency of credibility and other anomalies.

On site monitoring will compromise controlling presence and completeness of the research dossier and the informed consent forms, source data checks will be performed as described in the monitoring plan. Every participating center will be visited after the inclusion of the first ten patients and thereafter at least once every year. A monitoring plan is being developed.

11.3 Amendments

Amendments are changes made to the research after a favorable opinion by the accredited METC has been given. All substantial amendments will be notified to the METC and to the competent authority. Non-substantial amendments (typing errors and administrative changes) will not be notified to accredited METC and the competent authority, but will be recorded and filed by the sponsor.

11.4 Annual progress report

The investigator will submit a summary of the progress of the trial to the accredited METC once a year. Information will be provided on the date of inclusion of the first subject, numbers of subjects included and numbers of subjects that have completed the trial, unexpected problems and amendments

11.5 End of study report

The investigator will notify the accredited METC of the end of the study within a period of 8 weeks. The end of the study is defined as the 90th day after the last patients inclusion in the study. In case the study is ended prematurely, the investigator will notify the accredited METC within 15 days, including the reasons for the premature termination. Within one year after the end of the study, the investigator/sponsor will

submit a final study report with the results of the study, including any publications/abstracts of the study, to the accredited METC.

11.6 Public disclosure and publication policy

The study protocol will be registered before inclusion of the first patient on Clinicaltrials.gov. The results of the study will find their way into (inter-)national scientific journals and guidelines. We will submit analyses to scientific journals in the field of intensive care medicine as well as anesthesiology, since both ICU physicians and anesthesiologists apply ventilation in the ICU setting.

12. PUBLICATION POLICY

The PROVNet policy will be followed for publication. The intention is to publish the paper by the PROVE Network investigators. This means that there will be no names of individual researchers above a publication. The Principal Investigator is mentioned as the contact person, the members of the Steering Committee, the Writing Committee, and all local investigators of participating centers are summarized at the end of a manuscript or in the appendix depending on the journal policy. In this way <http://www.ncbi.nlm.nih.gov/pubmed/>

can link the names of all investigators to a publication. If a journal does not accept this, another approach will be discussed within the Steering Committee, and an explanation and conclusion will be posted on the website of the project.

From each participating center in the RELAX trial one local investigator per participating center will be on the authors list for publication. When a participating center includes more than the anticipated 82 patients per center, a second local investigator will be added to the authors list for publication. In case a participating center includes more than 164 patients, a third local investigator will be added to the authors list for publication.

APPENDIX I

Table 1. The Berlin definition for ARDS^{36,37}

Timing	Within 1 week of a known clinical insult, or new/worsening respiratory symptoms		
Chest imaging*	Bilateral opacities—not fully explained by effusions, lobar/lung collapse, or nodules		
Origin of edema	Respiratory failure not fully explained by cardiac failure or fluid overload; need objective assessment (e.g., echocardiography) to exclude hydrostatic edema if no risk factor present		
Oxygenation	Mild	Moderate	Severe
	$200 < \text{PaO}_2/ \text{FiO}_2 \leq 300$ mmHg	$100 < \text{PaO}_2/ \text{FiO}_2 \leq 200$ mmHg	$\text{PaO}_2/ \text{FiO}_2 \leq 100$ mmHg
	$26.7 < \text{PaO}_2/ \text{FiO}_2 \leq 40$ kPa with PEEP ≥ 5 cm H ₂ O or CPAP ≥ 5 cm H ₂ O	$13.3 < \text{PaO}_2/ \text{FiO}_2 \leq 26.7$ kPa with PEEP ≥ 5 cm H ₂ O	$\text{PaO}_2/ \text{FiO}_2 \leq 13.3$ kPa with PEEP ≥ 5 cm H ₂ O

* Chest radiograph or CT scan; ** If altitude higher than 1000 m, correction factor should be made as follows: $\text{PaO}_2/ \text{FiO}_2 \times (\text{barometric pressure}/760)$

Abbreviations: ARDS, acute respiratory distress syndrome; PaO₂, partial pressure of arterial oxygen; FiO₂, fraction of inspired oxygen; PEEP, positive end-expiratory pressure; CPAP, continuous positive airway.

DEFINITIONS

- APACHE (Acute Physiology and Chronic Health Evaluation) II: a point score ranging from 0–71, calculated from 12 measurements (age, temperature (rectal), mean arterial pressure, pH, heart rate, respiratory rate, sodium (serum), potassium (serum), creatinine, hematocrit, white blood cell count, GCS) higher scores correspond to more severe disease and higher risk of death
- MRC (Medical Research Council): grades strength in functional muscle groups in each extremity, ranging 0–5, a score of 5 corresponds to normal – healthy strength
- Pneumonia: new or progressive radiographic infiltrate plus at least two of the following: fever tympanic temperature > 38.5 , leukocytosis or leucopenia and/or purulent secretions

- Pneumothorax: air in the pleural space with no vascular bed surrounding the visceral pleura on chest radiograph or other kind of imaging suitable for diagnosis severe atelectasis
- Recruitment maneuver: increase of inspiratory pressure or the level of PEEP for at least 40 seconds
- SAPS (Simplified Acute Physiology Score) II: point score ranging from 0–163, as APACHE
- Severe atelectasis: at least complete lobar atelectasis of a lung on chest radiograph or other kind of imaging suitable for diagnosis severe atelectasis
- Severe hypoxemia: $\text{SpO}_2 < 88\%$ or $< \text{PaO}_2 7.3 \text{ kPa}$ more than 5 minutes or a rise of the oxygen fraction $> 60\%$ for more than 5 minutes related to a hypoxicemic event

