5.2 The 'restricted PEEP'-arm

Directly after start of invasive ventilation the PEEP level is set at 5 cm H₂O with an inspired oxygen fraction (FiO₂) between 0.21 and 0.6. The goal is to ventilate with the lowest possible PEEP level resulting in an acceptable level of oxygenation. For this, the operator, usually the attending ICU nurse, will reduce the level of PEEP in steps of 1 cm H₂O to a minimum level of 0 cm H₂O. Every 15 minutes the PEEP level is reduced with 1 cm H₂O, as long as the pulse oximetry reading shows a SpO₂ > 92% or the arterial blood gas shows a PaO₂ > 8 kPa, as illustrated in the flowchart (see **Figure 1**). Thereafter, ventilation continues with the lowest PEEP level at which the SpO₂ > 92% or PaO₂ > 8 kPa, using a FiO₂ of between 0.21 and 0.6. In case the SpO₂ drops below 92% or the PaO₂ drops below 8 kPa, brief periods of 5 minutes may be tolerated, first FiO₂ is increased up to maximum 0.6 before the level of PEEP is increased in steps of 1 cm H₂O until 5 cm H₂O. As soon as the patient stabilizes, again the level of PEEP is reduced in steps of 1 cm H₂O to a minimum level of 0 cm H₂O.

So-called 'down-titrations' of the PEEP level are allowed as often as wanted, but with a minimum of three 'down-titrations' per ICU nurse shift (i.e., every eight hours). This number is chosen to push nurses towards using the lowest possible PEEP level. We deliberately chose not to state a maximum for these 'down-titrations', as adjustments in ventilator settings, like FiO₂ and driving pressure, in the Dutch ICU setting are very frequent, occurring many more times than three times per shift – this is a safe process, and we assume it is the same for the PEEP level adjustments.

Patients are weaned from the ventilator (see: weaning) and tracheally extubated using the lowest PEEP level. In other words, the lowest PEEP level is used throughout the complete period of invasive ventilation. However, during pulmonary toileting and tracheal suctioning, bronchoscopic procedures, intra- or inter-ICU transport or any maneuver during which 'pre-oxygenation' with high FiO₂ is deemed beneficial, ICU nurses are allowed to increase the FiO₂ > 0.6, and preferably not the level of PEEP.

Pulmonary rescue: in case of severe hypoxemia, defined as a drop in SpO₂ below 88% or a drop in PaO₂ below 7.3 kPa, common causes such as a mucus plug

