requiring pulmonary toilet should be considered and treated, the FiO_2 level is increased up to 1.0 and the PEEP level is set back at 5 cm H_2O or more, both to a level left to the discretion of the attending physician. After solving the cause for the drop in SpO_2 or PaO_2 , the PEEP level is again ‘down–titrated’, following the same steps as described above. Development of atelectasis, or increases in the amount of atelectasis is not necessarily a reason for using a higher PEEP level, unless the SpO_2 drops below 92% or the PaO_2 drops below 8 kPa, and does not respond to increases in FiO_2 to maximal 0.6. If a patient develops ARDS, according to the Berlin definition for ARDS,^{36,37} the level of PEEP should always be increased to 10 cm H_2O , or more.

Hemodynamic rescue: in case a patient becomes hemodynamic unstable, meaning that more inotropes and/or vasoactive agents are needed, hemodynamic compromise due to increases in atelectasis could be considered. Then, for a short period of time (e.g., for 1 to 2 hours) the PEEP level can be set at 5 cm H_2O . After solving the hemodynamic problem, the PEEP level is again ‘down–titrated’.

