5.3 The ‘liberal PEEP’–arm

Directly after start of invasive ventilation the PEEP level is set at 8 cm H_2O with a FiO_2 between 0.21 and 0.6. The goal is to ventilate the patient mainly at this level of PEEP till tracheal extubation. For this, the operator will increase the level of PEEP, if a level of < 8 cm H_2O was used, to 8 cm H_2O in one single step (see **Figure 1**). Thereafter, ventilation continues with the PEEP level at 8 cm H_2O using a FiO_2 of between 0.21 and 0.6. In case the SpO_2 drops below 92% or the PaO_2 drops below 8 kPa, first FiO_2 is increased to maximum 0.6 before the level of PEEP is further increased.

Patients are weaned of the ventilator (see: weaning) and tracheally extubated using a PEEP level of 8 cm H_2O . However, during pulmonary toileting and tracheal suctioning, bronchoscopic procedures, intra– or inter–ICU transport or any maneuver during which ‘pre–oxygenation’ with high FiO_2 is deemed beneficial, ICU nurses are allowed to increase the $\text{FiO}_2 > 0.6$, and preferably not the level of PEEP. If preferred, the level of PEEP can be set at 5 cm H_2O for one to two hours directly before tracheal extubation, left to the discretion of the attending physician.

[figure not shown]
Pulmonary rescue: in case of severe hypoxemia, defined as a drop in SpO_2 below 88% or a drop in PaO_2 below 7.3 kPa, common causes such as a mucus plug requiring pulmonary toilet can be considered and treated, FiO_2 level is increased up to 1.0 to a level left to the discretion of the attending physician, if necessary the PEEP

level can be increased. After solving the cause for the drop in SpO₂ or the drop in PaO₂, FiO₂ and the level of PEEP is set back.

Hemodynamic rescue: in case a patient becomes hemodynamic unstable, meaning that more inotropes and/or vasoactive agents are needed, hemodynamic compromise due to increases in overdistension could be considered. Then, for a short period of time (e.g., for 1 to 2 hours) the PEEP level can be set at 5 cm H₂O. After solving the hemodynamic problem, the level of PEEP is again set back to 8 cm H₂O.

The goal is to ventilate patients in this arm with a PEEP level of 8 cm H₂O and only to adjust the PEEP level when deemed necessary. This reflects current ventilation practice in the Dutch setting, where the PEEP level is further increased to improve oxygenation, but decreased in case of hemodynamic compromise (see **Figure 1**).

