7.1.2 Secondary study parameters

Secondary study parameters include:

- ICU length of stay (LOS)
- Hospital LOS
- ICU mortality
- Hospital mortality
- 90-day mortality
- Incidence of development ARDS (APPENDIX I)
- Incidence of severe hypoxemia (APPENDIX I)
- Incidence of severe atelectasis, if a chest radiograph is obtained (APPENDIX I)
- Rescue therapies for severe hypoxemia or severe atelectasis
 - Recruitment maneuver (APPENDIX I)
 - Prone positioning
 - Bronchoscopy for opening atelectasis
- Incidence of pneumothorax, if a chest radiograph is obtained or other kind of imaging suitable for diagnosing pneumothorax is obtained (APPENDIX I)
- Incidence of pneumonia (APPENDIX I)
- The level of PEEP in the 'restricted PEEP'-arm and the 'liberal PEEP'-arm
- Days with use of hemodynamic support, defined as the number of ICU days with any use of vasopressors/inotropes for > 1 hour on a day
- Days with use of sedation, defined as the number of ICU days with any use of sedatives for > 1 hour on a day
- Therapeutic intervention scoring system (TISS)/ Nursing Activities Score (NAS)

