7.4 Data collection

- On admission and within the first 24 hours:

- Gender and age (male + years)
- Height and weight (cm + kg)
- Reason for ICU admission
- Reason for ventilation support
- Cause of respiratory failure
- APACHE II score and SAPS II score
- Respiratory status, on admission, and every day at a fixed time point until day 28:
 - Intubation status (if extubated: time of extubation)
 - Tracheostomy status (if tracheostomized: time of tracheostomy)
 - Invasiveness of ventilation (invasive, non-invasive, or intermittent ventilation via tracheostomy)
- Location of patient, every day at a fixed time point until day 28, and at day 90 (in ICU, hospital, other facility, or home) and life status (alive or deceased)
- Pulmonary complication, every day at a fixed time point until day 28 or discharge from ICU, whatever comes first:
 - ARDS (yes or no) (APPENDIX I)
 - Severe hypoxemia (yes or no) (APPENDIX I)
 - Pneumonia (yes or no) (APPENDIX I)
 - Severe atelectasis (yes or no) (APPENDIX I)
 - Pneumothorax (yes or no) (APPENDIX I)
- Need for rescue therapies for severe hypoxemia or severe atelectasis, every day at a fixed time point until day 28 or discharge from ICU, whatever comes first
 - Recruitment maneuver (yes or no) (APPENDIX I)
 - Prone positioning (yes or no)
 - Bronchoscopy for opening atelectasis (yes or no)
- Days with use hemodynamic support, every day at a fixed time point until day 28 or discharge from ICU, whatever comes first. Defined as the number of ICU days with any use of vasopressors/inotropes use for > 1 hour on a day (yes or no)
- Days with use of sedation, every day at a fixed time point until day 28 or discharge from ICU, whatever comes first. Defined as the number of ICU days with any use of sedatives for > 1 hour on a day (yes or no)
- ICU-acquired weakness, every day until day 28 or discharge from ICU, whatever comes first: Medical Research Council (MRC) score (APPENDIX I)⁴⁸

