8.2 Secondary endpoints for safety

Since we compare two ventilation strategies that are currently used in standard care, additional risks are not expected. Furthermore, the study population consists of critically ill patients, with a high incidence of death or life-threatening events due to the severity of their illness (the hospital mortality in ventilated ICU patients is 21% ³⁴). Therefore, we propose to report the secondary endpoints of this trial, which incorporate ventilation specific complications, in a line listing two times per year to the METC to monitor safety of both treatment strategies. The METC will receive a line listing of the secondary endpoints incorporating ventilation specific ventilation complications (see below). These endpoints will be specified per study arm in the line listing without disclosing the specific arms.

Those ventilation specific complications include:

- ICU mortality
- Incidence of development of ARDS
- Incidence of severe hypoxemia
- Incidence of rescue therapy for severe hypoxemia and/or severe atelectasis:
 - Recruitment strategies
 - Prone positioning
 - Bronchoscopy for opening atelectasis

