8.3 Data Safety Monitoring Board (DSMB)

An DSMB will be installed to monitor safety and the overall conduct of the trial. The DSMB will compose of 4 individuals who will be invited, one of which will be the chairman.

- The DSMB will first meet after inclusion of the first 150 patients, approximately 6 months after the first patient is enrolled.

- Subsequent to this meeting the DSMB will meet virtually every 6 months
- The DSMB will review the overall status of the program, number of patients enrolled overall and in each center, adherence to the protocol overall and by each center.
- The DSMB will monitor safety of both ventilation strategies by monitoring the secondary endpoints of ventilation specific complications.
- The following DSMB individuals will be invited:
 - [name], MD PhD, St James's University Hospital, Dublin, Ireland
 - [name], MD, Universita degli Studi dell'Insubria, Varese, Italy
 - [name], MD PhD, Canberra Hospital, Garran, Australia
 - Prof. [name], MD PhD, Hospital de Sabadell, Sabadell, Spain

The report and/or advice of the DSMB will only be sent to the sponsor of the study, the Academic Medical Center. Should the sponsor decide not to fully implement the advice of the DSMB, the sponsor will send the advice to the reviewing METC, including a note to substantiate why (part of) the advice of the DSMB will not be followed.

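### Read literally, the Appendix I definition of a recruitment maneuver covers the PEEP reset that 5.2 instructs for severe hypoxemia in a patient below 5 cm H2O, so this component of the rescue endpoint can be influenced by allocation

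*Protocol*

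**What the plan says.** The definition in Appendix I is "Recruitment maneuver: increase of inspiratory pressure or the level of PEEP for at least 40 seconds". The only threshold is the minimum duration.

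The definition feeds three uses:
- **Secondary endpoint (7.1.2).** It is one of three components under "Rescue therapies for severe hypoxemia or severe atelectasis", beside prone positioning and bronchoscopy. It is recorded daily under 7.4 as "Recruitment maneuver (yes or no) (APPENDIX I)".
- **METC listing (8.2).** Recruitment strategies appear under "Incidence of rescue therapy for severe hypoxemia and/or severe atelectasis", reported twice a year by arm without naming the arms.
- **DSMB (8.3).** "The DSMB will monitor safety of both ventilation strategies by monitoring the secondary endpoints of ventilation specific complications".

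The arms differ in how PEEP responds to severe hypoxemia. In the restricted arm, 5.2 instructs that "the PEEP level is set back at 5 cm H_2O or more, both to a level left to the discretion of the attending physician". In the liberal arm, 5.3 is permissive: where needed, the PEEP "level can be increased. After solving the cause for the drop in SpO₂", and the text goes on to restore the settings.

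Two other places treat a recruitment maneuver as a separate act. Section 6.1 leaves the decision to perform one to the attending physician. In Appendix III, patient B's PEEP is first returned to 5 cm H2O and a recruitment maneuver is then performed as a further step. Patient C's PEEP is raised from 5 to 10 cm H2O for falling saturation, and this is not called a recruitment maneuver.

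**The concern.** The restricted arm aims to keep patients below 5 cm H2O. For such a patient, the reset under 5.2 is a PEEP increase that normally lasts far longer than 40 seconds. A site applying Appendix I as written would tick the recruitment-maneuver box for an act that the allocated algorithm requires. In the liberal arm, the same event handled with FiO2 and clearance of secretions would leave the box empty.

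Two problems follow. The between-arm comparison of this component can reflect the algorithm rather than a need for rescue. Sites can also code the same event differently, depending on whether they follow the literal definition or the sense of 6.1 and Appendix III. The trial is open label, and a daily yes/no item does not show which reading was used. PEEP is recorded once a day at a fixed time (7.4.1), which is too coarse to reconstruct it afterwards. An excess in one arm could then be read by the METC or DSMB as a safety signal.

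**Working it through.** **Step 1: does the protocol-directed act meet the definition and fall within the endpoint?**

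| Act | PEEP increase of at least 40 s? | Response to severe hypoxemia (7.1.2 heading)? | Status in the protocol |
|---|---|---|---|
| Restricted arm, pulmonary rescue, patient below 5 cm H2O (5.2) | Yes | Yes | Instructed |
| Restricted arm, pulmonary rescue, patient already at 5 cm H2O (5.2) | Only if raised above 5 | Yes | Discretionary |
| Restricted arm, stepwise increase at SpO2 below 92% (5.2) | Yes | No | Instructed |
| Liberal arm, pulmonary rescue (5.3) | If done | Yes | Optional |
| Liberal arm, further increase at SpO2 below 92% after FiO2 0.6 (5.3) | Yes | No | Foreseen |

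The first and fourth rows carry the point: the same clinical event produces an instructed qualifying act in one arm and an optional one in the other. The heading of 7.1.2 does not exclude the first row, because that reset is a response to severe hypoxemia. One limit applies. Appendix I requires more than 5 minutes below 88% or 7.3 kPa (or FiO2 above 60% for that long), whereas the 5.2 trigger has no duration, so some brief episodes drop out.

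**Step 2: how large could the artefact be?** There is no figure in the documents to reproduce, because they give no rate of severe hypoxemia, of maneuvers or of resets. The following is an illustration on assumptions.

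- h = proportion with severe hypoxemia, equal in both arms: 20% (range 10% to 30%).
- r = proportion of those who receive a deliberate maneuver, equal in both arms: 20%.
- m = proportion of restricted-arm cases in which PEEP is raised: 90%.
- d = proportion of liberal-arm cases in which PEEP is raised: 20%, 50% or 80%.
- n = 445 per arm, the analysed number in 4.4.

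If maneuvers and PEEP increases occur independently, the counted proportion is h × [1 − (1 − r)(1 − PEEP-raised proportion)].

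- Restricted: 0.20 × [1 − 0.8 × 0.1] = 0.20 × 0.92 = 18.4%.
- Liberal, d = 20%: 0.20 × [1 − 0.8 × 0.8] = 0.20 × 0.36 = 7.2%.
- Liberal, d = 50%: 0.20 × [1 − 0.8 × 0.5] = 0.20 × 0.60 = 12.0%.
- Liberal, d = 80%: 0.20 × [1 − 0.8 × 0.2] = 0.20 × 0.84 = 16.8%.

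The ratios are 0.92/0.36 = 2.56, 0.92/0.60 = 1.53 and 0.92/0.84 = 1.10, and h cancels. At d = 90% the ratio is 1.00.

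The chance of a two-sided p below 0.05 is Φ[(difference − 1.96 × SE0)/SE1], with SE0 pooled and SE1 unpooled. For 18.4% vs 12.0%, SE0 = 0.0241 and SE1 = 0.0240, so Φ[(0.064 − 0.0472)/0.0240] = Φ(0.70) = 76%.

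| h | d = 20% | d = 50% | d = 80% |
|---|---|---|---|
| 10% | 93% | 44% | 6% |
| 20% | 99.9% | 76% | 9% |
| 30% | about 100% | 93% | 13% |

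**Step 3: is the direction fixed?** No. The value of m depends on how many restricted-arm patients are below 5 cm H2O when they become hypoxemic. With m = 50% and d = 80%, the ratio is 0.60/0.84 = 0.71, the other way round.

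**The case against.** The strongest reply is that the protocol, read as a whole, already says what it means. Section 6.1 makes a recruitment maneuver a physician's decision, whereas titration is a rule followed by the nurse, and the Appendix III examples keep the two apart. On that reading Appendix I only adds a minimum duration to an act understood elsewhere. This shows the intent and makes correct coding at many sites plausible. It does not remove the conflict, because the data item in 7.4 points to Appendix I rather than to 6.1. CRF completion instructions are not shown, so actual coding is unknown.

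It is also fair that contamination is not confined to one arm. Section 5.3 allows PEEP increases for severe hypoxemia, and patient C was already at 5 cm H2O when desaturation began. The imbalance therefore depends on practice.

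Two stronger readings are tempting. A reader might infer that ordinary titration floods the endpoint: 5.2 asks for at least three down-titrations per eight-hour shift, and any that fail are reversed by a PEEP increase ("before the level of PEEP is increased in steps of 1 cm H₂O until 5 cm H₂O"). The documents do not support this. Those steps are triggered at SpO2 below 92% or PaO2 below 8 kPa, outside the severe-hypoxemia or atelectasis heading, and a patient already at 0 cm H2O cannot be stepped down. A reader might also infer that the whole rescue comparison is uninterpretable. It is not, because prone positioning and bronchoscopy contain no PEEP element.

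**Conclusion.** The conflict is real but narrow. Taken literally, Appendix I counts the pulmonary-rescue reset of 5.2 as a recruitment maneuver in a restricted-arm patient below 5 cm H2O, while the liberal-arm counterpart is optional. The recruitment-maneuver component can therefore be influenced by allocation and coded inconsistently between sites. The documents do not support the stronger statement that allocation drives it.

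The illustration shows anything from a ratio of 2.56 to a negligible 1.10, or none. It rests on equal severe hypoxemia and equal true maneuvers in both arms, on literal coding at every site, and on PEEP being raised in 90% of restricted-arm cases.

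The primary endpoint is unaffected. The METC listing shows severe hypoxemia and ICU mortality separately, which gives context for any imbalance, and 8.3 attaches no stopping rule to this item. The definition should be corrected, since it serves a secondary endpoint that is reported by arm for safety.

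**What to change.** Reconcile Appendix I with 5.2, 5.3, 6.1 and Appendix III. For endpoint coding, define a recruitment maneuver as a deliberate, temporary increase of inspiratory pressure or PEEP performed to reopen lung tissue. State that PEEP changes made under the titration or rescue rules of 5.2 and 5.3 are not counted. Use the same definition in the CRF and in the METC and DSMB listings. If algorithm-directed PEEP increases are of interest, record them as a separate item.

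The cost is one definition line, plus one CRF checkbox if the separate item is wanted. Clinical management does not change.
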